5.2.8 Discontinuation from trial intervention

See Section 7.2.8.

6 RANDOMISATION AND BLINDING

Once consent has been obtained, and following eligibility assessment, eligible participants will be recruited and randomised. Participants will be randomised 1:1 to one of the 2 intervention groups (*Comirnaty*[®] standard dose, *Comirnaty*[®] fractional dose) stratified by the primary vaccine received (*BBIBP-CorV*[®], *Comirnaty*[®] or Gam-COVID-Vac[®]) and age (<50 and \geq 50 years). A secure, password-protected web-based randomisation schedule will be provided by an independent statistician from the Melbourne Children's Trial Centre at the Murdoch Children's Research Institute. Blocked randomisation will be used with random blocks of permuted length. To ensure there are even numbers by primary vaccine and age group, participants will be recruited until the number required in each stratum has been reached.

40% of participants from each group will be included in the CMI subgroup analysis. The strata that will be used for CMI analysis will be identified at this time, and measures will be taken to ensure that the age strata (<50 and \geq 50 years) are equally represented in this group with a separate randomisation list. Only 10-20 CMI samples can be processed per day. We will therefore recruit the first 10-20 participants to participate in this sub study per day. Daily recruitment for the sub study will be stopped once the maximum number is reached.

6.1 Concealment mechanism

Randomisation will be stratified according to age (<50 and \geq 50 years) and primary vaccine (*BBIBP-CorV*[®] or *Comirnaty*[®]). Using REDCap the participants will be randomised to one of two groups in a 1:1 dose allocation ratio. (see table below).

Primary vaccines	Age	Booster vaccine	Dose given
Sinopharm,	<50	Pfizer-BioNTech	30µg
AstraZeneca, or		Pfizer-BioNTech	15µg
Sputnik V	>=50	Pfizer-BioNTech	30µg
		Pfizer-BioNTech	15µg

Study staff (unblinded vaccinator) involved in administering the vaccine will use REDCap to receive the information on the participant's randomisation number and vaccine dose so they will be aware of which vaccine the participant is receiving. The participants themselves will remain blinded to their vaccine dose (until day 28 post vaccination). Study staff involved in assessing reactogenicity will be blinded to each participant's vaccine dose until 28 days post vaccination, as this variable will be hidden in REDCap for blinded study staff. Study staff involved in assessing immunogenicity outcomes will remain blinded during the analysis of specimens.

Vaccines will be prepared out of sight of the participant and the blind will be maintained by applying masking tape over the vaccine syringe, so the study participant can't see the volume.

Only the study nurse (unblinded vaccinator) administering the vaccine will be aware of which vaccine is given to the study participant.

6.2 Breaking of the trial blind 6.2.1 On trial

The study will be blinded for the first 28 days only. In the unlikely event that it becomes necessary to unblind during this period that decision will be taken by the PI, and the subject and physicians who may be caring for the subject will be made aware of the dose allocation.

7 TRIAL VISITS AND PROCEDURES

7.1 Schedule of assessments

	Visit 1	Visit 2	Visit 3	Visit 4	Visit 5	Visit 6	Visit 7	Visit 8	Visit 9
Location	At health centre	Phone call	Phone call	At health centre	Phone call	At health centre	At health centre	At health centre	At health centre
Timing	Day 0	Day 1	Day 7	Day 28	3 months	6 months	12 months	18 months	24 months
Visit			+ 3	+ 7	+/-	+/-	+/-	+/-	+/-
window			days	days	14 days	14 days	30 days	30 days	30 days

Informed consent	Х								
Eligibility confirmatio n	Х								
Randomisat ion	Х								
Blood sampling	Х			х		Х	Х	Х	Х
Vaccination	Х								
Vital signs	Х								
Issue diary card, ruler and thermomet er	Х								
Collect	Х								
diary card	(daily)								
Documenta tion of Solicited AE	Х	Х	Х						
Documenta tion of unsolicited AE	Х	Х	х	х					
Documenta tion of medically attended AE	Х	Х	Х	Х	Х				
Documenta tion of SAE	Throug	hout study	y period						
Documenta tion of confirmed breakthrou gh COVID- 19 infection	Throug	hout study	y period						

7.2 Description of procedures

7.2.1 Visit 1 (Day 0)

Informed consent must be signed by both participant and study doctor or nurse.

Participant eligibility must be confirmed prior to randomisation and on the same date as administration of the investigational product.

Eligibility must be confirmed by a study doctor or study nurse. Randomisation must be completed by the unblinded vaccinator who will document the participant's randomisation number on the enrolment log.

Study staff will administer a Visit 1 questionnaire documenting demographic information, height and weight, dates and type of primary COVID-19 vaccine, prior confirmed SARs-Cov-2 infection(s) documented in medical records, any comorbidities and concomitant medication.

The following vital signs will be recorded by a study doctor or study nurse prior to vaccination: temperature, pulse rate, respiratory rate, and blood pressure.

Prior to vaccination, for all participants, 5mL of blood will be collected and processed according to the SOP. CMI participants will have an additional 25ml collected and processed for Quantiferon analysis and PBMC separation and storage.

Following randomisation, the unblinded vaccinator will administer the applicable vaccine to the participant.

Study staff will provide the participant with a hard copy reactogenicity diary card or email them a REDCap survey form. Study staff will instruct the participant on how to complete the diary card for the day of vaccination and seven days following vaccination. Patients who complete a hard copy diary card will be asked to bring it to their day 28 visit so that the information can be entered in the REDCap database.

Study staff will provide the participant with a thermometer and ruler and detailed instructions on how to use these for measuring temperature and potential erythema and induration. Study staff will provide the participant with a schedule of visit appointments and instruct the participant on how to contact the study staff in case of any SAE or symptoms suggestive of COVID-19.

Study staff will keep the participant under observation for minimum 15 minutes and document any immediate adverse events.

7.2.1 Visit 2 (Day 1)

Study staff will contact the participant by phone approximately 24 hours after vaccination to review and document adverse events.

7.2.2 Visit 3 (Day 7)

Study staff will contact the participant by phone one week after vaccination. If participants have a hard copy card study staff will ask participants to read the details over the phone or send a picture of their hard copy diary card (with the name obscured) for review. If the participant completed the REDCap

diary card, study staff will review it with them to confirm that all symptoms are captured. Study staff will also document any significant, unexpected, serious or unusual adverse events on the AE CRF.

7.2.3 Visit 4 (Day 28)

An in-person visit will be conducted 28 days following vaccination. Participants with hard copy diary cards will be asked to bring the card to this visit for collection. All Unsolicited Adverse Events will be documented. Study staff will also document any new information regarding solicited adverse events with onset up to 7 days following vaccination, such as resolution. The participant will be informed which vaccine dosage they received based on entry into the CRF by the unblinded staff member. For all participants, 5mL of blood will be collected in an SST tube. For participants in the CMI subset, 5mL of blood for Quantiferon test will be collected in a heparinised tube, and 20mL of blood for PBMC will be collected in a heparinised tube. Blood samples will be kept at room temperature and transferred to the laboratory within 3 hours of collection. SST tubes should be kept cold (around 4 degrees) if not transferred within 3 hours.

7.2.4 Visit 5 (3 Months)

Study staff will contact the participant by phone and document information on any medically attended AE or SAE.

Study staff will also document any new information regarding unsolicited adverse events with onset up to 28 days following vaccination, such as resolution.

7.2.5 Visit 6 (6 Months)

For all participants, 5mL of blood will be collected in an SST tube. For participants in the CMI subset, 5mL of blood for Quantiferon test will be collected in a heparinised tube, and 20mL of blood for PBMC will be collected in a heparinised tube. Blood samples will be kept at room temperature and transferred to the laboratory within 3 hours of collection. SST tubes should be kept cold (around 4 degrees) if not transferred within 3 hours. An SMS will be sent to participants monthly between Visit 6 and Visit 7 to check for any breakthrough infections and AE/SAEs.

7.2.6 Visit 7 (12 Months)

For all participants, 5mL of blood will be collected in an SST tube. For participants in the CMI subset, 5mL of blood for Quantiferon test will be collected in a heparinised tube, and 20mL of blood for PBMC will be collected in a heparinised tube. Blood samples will be kept at room temperature and transferred to the laboratory within 3 hours of collection. SST tubes should be kept cold (around 4 degrees) if not transferred within 3 hours. Participants will be invited to participate for a further 12 months and will be re-consented for Visit 8 and 9. (For those participants who have already attended their 12 month visit, a phone call will be made and consent signed at Visit 8). All participants will receive a gift card for 50.000 Mongolian Tugrik (~14 USD) at 12 months as some visits will be completed at time of extension. An SMS will be sent to participants monthly between Visit 7 and Visit 8 to check for any breakthrough infections and SAEs.

7.2.7 Visit 8 (18 Months)

For all participants, 5mL of blood will be collected in an SST tube. For participants in the CMI subset, 5mL of blood for Quantiferon test will be collected in a heparinised tube, and 20mL of blood for PBMC will be collected in a heparinised tube. Blood samples will be kept at room temperature and transferred to the laboratory within 3 hours of collection. SST tubes should be kept cold (around 4 degrees) if not transferred within 3 hours. An SMS will be sent to participants monthly between Visit 8 and Visit 9 to check for any breakthrough infections and SAEs. Participants will be asked if they have received another covid vaccine since their last visit.

7.2.8 Visit 9 (24 Months)

For all participants, 5mL of blood will be collected in an SST tube. For participants in the CMI subset, 5mL of blood for Quantiferon test will be collected in a heparinised tube, and 20mL of blood for PBMC will be collected in a heparinised tube. Blood samples will be kept at room temperature and transferred to the laboratory within 3 hours of collection. SST tubes should be kept cold (around 4 degrees) if not transferred within 3 hours.

Participants who complete the 24-month study period will receive a gift card for 50.000 Mongolian Tugrik (~14 USD). If they request, results of their tests will be shared and discussed with them by a member of the study team at any visit if available. Participants will be asked if they have received another Covid-19 vaccine since their last visit.

7.2.9 Unscheduled visits

If any participant develops symptoms of Covid-19 or tests positive on a rapid antigen test (RAT), they will be instructed to contact the Study Team and to get a PCR test at the nearest facility. If the test (RAT or PCR) is positive the Study Team will seek to obtain a specimen for virology, either residual from the specimen that tested positive, or an additional swab once the positive result is known. One month after the positive test a 5ml blood sample will be collected and serum stored for future serological analysis if the participant consents. Participants will be reimbursed for unscheduled visits. The participant will otherwise continue with scheduled study visits. The virology sample will be tested at the National Centre for Communicable Diseases in Mongolia. If there are a large number of breakthrough infections, all severe cases and a proportion of mild cases will be prioritised for sequencing. The study team will maintain telephone contact daily with the participant for the course of his/her illness and fully document all telephone calls. With the subject's permission the Team will seek clinical data from the health care providers or hospital in the event that the subject becomes clinically ill. If breakthrough infections are not being captured using RAT or PCR testing, an additional detection method to measure IgG antibodies specific for SARS-CoV-2 nucleocapsid (N) protein in serum (in-house ELISA) may be used to identify if an infection has occurred. Any confirmed breakthrough infections will be documented until the end of the study (Visit 9- 24 months).

7.2.10 Withdrawal of consent - participant withdraws from all trial participation

A participant has the right to withdraw from the trial at any time and for any reason and is not obliged to give his or her reasons for doing so. The Investigator may withdraw the participant at any time in the

interests of the participants' health and well-being. In addition, the participant may withdraw/be withdrawn for any of the following reasons:

- Administrative decision by the Investigator
- Ineligibility (either arising during the trial or retrospectively, having been overlooked at screening).
- Significant protocol deviation
- Participant non-compliance with study requirements

The reason for withdrawal will be recorded in the CRF. If the participant has an AE at the time of withdrawal, appropriate follow-up visits or medical care will be arranged, with the agreement of the participant, until the AE has resolved, stabilised or a non-trial related causality has been assigned. If a participant withdraws from the study, storage of samples and data collected before their withdrawal will still be used in the analysis, unless the participant specifically requests otherwise.

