3.2.2 Secondary outcomes

Immunogenicity

Functional antibody – All samples at all timepoints will be assayed using the GenScript cPass

SARS-CoV-2 Neutralization Antibody detection kit for both the Wuhan strain and Omicron variant RBD antigen in Mongolia.

Neutralizing antibody - A fraction of samples (20%) will be assessed using a SARS-CoV-2 microneutralisation assay undertaken at the PDI, Melbourne. Assays will be done at all six timepoints to the Wuhan strain (first generation COVID vaccine) and for 2 Variants of Concern.

Cellular immunity - Cellular immunity will be assessed on a subset of 40% of participants, with samples collected at six timepoints: baseline, 28 days, 6 months, 12 months, 18 months and 24 months post-vaccination as follows:

- *QuantiFERON Human IFN-γ* SARS-CoV-2 (Qiagen) will be performed using heparinised whole blood
- Peripheral blood mononuclear cells (PBMCs) will also be isolated by density gradient centrifugation within 12 hours of collection and stored in liquid nitrogen at MCRI. Assays performed will include IFN-γ Elispot, intracellular cytokine assays (flow cytometry) and multiplex cytokine assays.
- To assess the impact of prior natural exposure on boosting regimens by comparing antibody responses between those who do/don't report a previous COVID infection.

Safety

• All solicited adverse events (AE) will be collected for 7 days, all unsolicited AE will be collected for 28 days, and all medically attended AE will be collected for 3 months. SAE will be collected throughout the follow up period of 24 months.

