4 TRIAL DESIGN

4.1 Overall design

This clinical trial will be a single blind, randomised study to determine the immunogenicity and reactogenicity of booster doses of SARS-CoV-2 vaccines in adults. Both fractional and standard doses will be tested.

The groups are described below. The trial intervention will be a single booster dose of vaccine: -

Primary vaccine	Booster vaccines
Sinopharm (BBIBP-CorV ®)	1. Pfizer-BioNTech (BNT162b2, or Comirnaty®) Standard
	dose (30µg) n= 200
	2. Pfizer-BioNTech (BNT162b2, or Comirnaty®) Fractional
	dose (15µg) n= 200
AstraZeneca (ChAdOx1-S, or	3. Pfizer-BioNTech (BNT162b2, or Comirnaty®) Standard
Vaxzevria®)	dose (30µg) n= 100
	4. Pfizer-BioNTech (BNT162b2, or Comirnaty®) Fractional
	dose (15µg) n= 100
Sputnik V (Gam-COVID-Vac®)	5. Pfizer-BioNTech (BNT162b2, or Comirnaty®) Standard
	dose (30µg) n= 100
	6. Pfizer-BioNTech (BNT162b2, or Comirnaty®) Fractional
	dose (15µg) n= 100

The trial intervention will be given 6 or more months after the primary vaccine schedule. The groups size will be either 200 (Sinopharm groups) or 100 (AstraZeneca and Sputnik groups) individuals with an even spread of participants above and below 50 years in each group. The Sinopharm vaccinee impact is of greater importance to Mongolia as this is the main vaccine used for the primary series in Mongolia. In addition, Sinopharm is the least effective of the 3 vaccines used, so we expect to see evidence of more breakthrough cases and therefore a wider range of pre-booster immunity levels. The trial will be conducted at multiple sites (health centres, hospital or vaccination clinics) in Ulaanbaatar and provincial sites.

The trial will be single blind. The participants and those evaluating reactogenicity will be blinded to the vaccine dose allocation for the first 28 days following vaccination. After that, both the clinical investigators and potentially participants will be aware of their investigational product dose allocation. Immunologists and laboratory staff will remain blinded to the investigational product dose allocation.

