11.2 Population to be analysed

Analysis of this trial is planned on both the intention-to-treat population (ITT), with all participants to be analysed in the group they were randomised to, as well as on the per-protocol (PP) population, consisting of participants who adhered to the study protocol. However, it is expected that withdrawn participants may not have data to contribute at all time points as blood samples may not be collected after the time of their withdrawal.

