6.8 ADHERENCE AND PROTOCOL DEVIATIONS

Adherence to the intervention is defined as receiving a trial booster vaccination on Day 0. The number and percent of participants who adhered will be presented by study group.

Pre-defined major protocol deviations (with a direct bearing on the primary outcome) are:

- Receiving a 4th dose prior to the Day-28 visit
- Inclusion and randomisation of an ineligible person
- Receiving the wrong trial vaccination
- Day-28 visit occurring outside of the specified time window (between Day 28 and 35 [inclusive], with Day 0 being the day of trial vaccination)

All protocol deviations will be classified as minor or major prior to unblinding. Major protocol deviations are those that are deemed to significantly affect the rights or safety of a trial participant, or the reliability, accuracy, and robustness of the data. The number and percentage of patients with major and minor protocol deviations will be summarised by study group (as per randomisation), with details of type of deviation provided.

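### Protocol 7.2.10 lets investigators end all follow-up of vaccinated participants for reasons other than consent, which creates avoidable missing data and leaves their 24-month SAE collection unsecured

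*Protocol*

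**What the plan says.** Protocol 7.2.10 carries the heading phrase "participant withdraws from all trial participation". Besides the participant's own right to withdraw and the investigator's power to withdraw someone for health and well-being, it permits withdrawal for four further reasons: an administrative decision by the investigator, "Ineligibility (either arising during the trial or retrospectively, having been overlooked at screening", "Significant protocol deviation" and "Participant non-compliance with study requirements". The wording is permissive. Samples and data obtained before withdrawal stay in the analysis unless the participant objects. An AE present at withdrawal is followed up with the participant's agreement. Nothing is said about later blood samples or new SAEs.

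Protocol 11.2 plans an intention-to-treat analysis "with all participants to be analysed in the group they were randomised to" and a per-protocol analysis, and accepts that withdrawn participants may lack later samples. Protocol 3.2.2 states that "SAE will be collected throughout the follow up period of 24 months", and 8.2 follows SAEs for the trial's duration.

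SAP 6.8 lists "Inclusion and randomisation of an ineligible person" among the major deviations, with the wrong vaccination, a 4th dose before the Day-28 visit and an out-of-window Day-28 visit. These are to be summarised; no exclusion rule is given. SAP Tables 10, 12 and 13 analyse all randomised participants, as randomised, who have complete data. SAP 6.11 treats withdrawals as missing data. Table 14 applies imputation only as a sensitivity analysis above 5% missingness.

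On blinding after Day 28, protocol 4.1 says: "After that, both the clinical investigators and potentially participants will be aware of their investigational product dose allocation".

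**The concern.** When treatment is ongoing, withdrawing an ineligible or non-adherent participant can at least stop exposure. Here exposure is complete on Day 0, so withdrawal can only remove later outcomes. The people open to removal overlap with those whom SAP 6.8 flags and keeps: ineligible persons, wrong vaccinations and early 4th doses. Such people may respond differently from the rest. After Day 28 the clinical investigators know the dose, so later losses could differ by arm.

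Two things are at stake. The first is the later immunogenicity comparisons, where losses related to both arm and response would bias a complete-case estimate and could stay below the imputation threshold. The second is safety: a person vaccinated despite an exclusion criterion is someone whose later SAEs the trial should want, and 7.2.10 describes no route for collecting them.

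**Working it through.** **1. What withdrawal can change.** Protocol 7.1 and 7.2.1 put eligibility confirmation, randomisation and vaccination on Day 0. Ineligibility found later therefore concerns people already randomised and normally already vaccinated. What remains is blood sampling (Day 28 and Months 6, 12, 18 and 24) and safety contact.

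**2. Passages side by side.**

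- *Level of withdrawal.* The footnote to the SAP 6.6 disposition list asks for withdrawal from intervention, from follow-up, or from both. Protocol 7.2.10 offers only total withdrawal. Protocol 5.2.8 sends discontinuation of intervention to 7.2.8, which is now the 24-month visit.
- *Ineligibility during the trial.* Protocol 4.4.2 excludes people on immunosuppressive medication, while 5.2.7 records such therapy to 24 months, which implies continued follow-up. Under 7.2.10, starting it could be read as ineligibility arising during the trial. That is an inference.
- *SAEs.* Protocol 3.2.2 and 8.2 run to 24 months or the trial's end. Protocol 7.2.10 covers only an AE present at withdrawal.
- *Breakthrough infection.* SAP Table 15 counts every randomised participant without a positive test as uninfected, so a withdrawn participant would be counted as infection-free to each timepoint. Table 16 (rates) censors at the last attended visit and is less exposed.

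**3. Power.** Inputs from protocol 11.1: 95% seroresponse in both arms, margin 10 points, two-sided 95% interval. With a normal approximation,

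power = Φ(0.10 / √(2 × 0.95 × 0.05 / n) − 1.96).

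n = 100 gives 90.05% and n = 200 gives 99.57%, which reproduces the stated 90% and >99%. The documents give no withdrawal rate. Assuming 2%, 5% or 10% lost per arm, power is 89.5%, 88.5% or 86.8% from 100, and 99.5%, 99.4% or 99.2% from 200. Precision is not the problem; selection is.

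**4. Selection at Day 28, worst case.** All counts here are assumed. The interval is the score-based one cited in protocol 11.3 (Newcombe, from Wilson limits l and u; 1 = fractional, 2 = standard):

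lower = (p1 − p2) − √[(p1 − l1)² + (u2 − p2)²].

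For 352/400 vs 380/400: p1 = 0.880, l1 = 0.8445, p2 = 0.950, u2 = 0.9674. The difference is −0.070 and the root term is 0.0395, so the lower limit is −10.95 points.

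| Fractional vs standard | Loss | Lower limit (points) |
|---|---|---|
| 352/400 vs 380/400 | none | −10.95 |
| 352/395 vs 380/400 | 5 fractional non-responders | −9.76 |
| 351/395 vs 380/400 | 5 fractional, 4 of them non-responders | −10.03 |
| 352/395 vs 380/395 | 5 non-responders from each arm | −10.85 |
| 380/400 vs 380/400 | none (protocol's 95% in both arms) | −3.13 |
| 380/395 vs 380/400 | 5 fractional non-responders | −1.74 |
| 90/100 vs 95/100 | none | −12.96 |
| 90/97 vs 95/100 | 3 fractional non-responders | −9.71 |
| 90/97 vs 95/97 | 3 non-responders from each arm | −12.25 |

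Five of 400 is 1.25% of an arm, below the 5% threshold. The conclusion at 400 per arm changes only if all five losses are fractional-arm non-responders and none come from the standard arm. If withdrawal were unrelated to response, the chance that five fractional losses are all non-responders would be about 0.12⁵ ≈ 0.00002. The SAP's main model is an adjusted identity-link binomial regression, so these unadjusted limits only illustrate the mechanism.

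**5. What an amendment can still reach.** The synopsis says recruitment is complete and took about 4 months; protocol 7.2.6 says some participants have already attended Month 12 (window ±30 days). Those were enrolled at least about 11 months earlier, so the last enrolled are at least about 11 − 4 = 7 months in. Day 28 is past for everyone and, on the same reckoning, so is the Month-6 window. What remains is Month 12 for some, Months 18 and 24, and SAE follow-up.

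**The case against.** A reader might infer that 7.2.10 contradicts intention-to-treat. The documents do not support that. Withdrawal is optional, nobody leaves their randomised group, earlier data are kept, 7.2.12 bars replacement, and both protocol 11.2 and SAP 6.11 foresee the missing data. The analysis sets require complete data, not samples taken after withdrawal.

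A reader might also infer a contradiction with the treatment-policy strategy. At Day 28 that strategy covers only SARS-CoV-2 infection; at Months 6 and 12 it covers infection, a self-initiated 4th dose and rescue vaccination. Ineligibility, wrong vaccination and non-compliance are not intercurrent events. The overlap arises only where one event is both, such as a 4th dose before Day 28 followed by withdrawal before Month 6.

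Nor does any sentence say that SAE follow-up stops. It is inferred from silence, and 8.2 read alone points the other way.

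The Day-28 reversal is weak as evidence. Before that visit participants and reactogenicity assessors are masked and no Day-28 antibody result exists, so there is little reason for losses to be confined to one arm's non-responders. An out-of-window Day-28 visit already has its sample.

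All of this stands, and it limits the strength of the point. It does not remove it: allowing for missing data does not justify creating it by discretion when exposure cannot change, and after Day 28 the masking argument no longer applies to clinical investigators.

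**Conclusion.** The point holds in a limited form. Protocol 7.2.10 permits discretionary removal of vaccinated participants, which brings no reduction in exposure. It weakens the as-randomised analyses through avoidable missing data and fails to secure the 24-month SAE record for people whose safety data matter. It is worth correcting, but it is not a flaw that overturns the primary analysis.

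The size is unknown, because the documents give no withdrawal rate. Under assumed losses of 2% to 10%, the power cost is at most about 3 points at 100 per group and under 1 point at 200. The Day-28 reversal needs an extreme, one-sided loss and should not be presented as the expected effect. The real exposure is at the later visits, where the dose is known to clinical investigators; no figure can be put on it from the documents. The safety part rests on reading silence in 7.2.10 as a gap.

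**What to change.** Amend 7.2.10 to separate withdrawal of consent from investigator decisions:

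- Remove administrative decision, ineligibility, significant deviation and non-compliance as grounds for ending follow-up of a vaccinated participant. Leaving the administrative ground in place would keep the broadest discretion open.
- State that such participants stay in scheduled blood sampling and SAE follow-up unless they withdraw consent, and are analysed as randomised.
- Identify them through the SAP 6.8 deviation flag and the per-protocol set in protocol 11.2, not by removal.
- Leave the participant's right to withdraw and the health and well-being provision unchanged.
- Correct the cross-reference in 5.2.8.

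The cost is one paragraph of amendment and a note to sites. No visits are added and no sample-size figure changes. The downside is that sites keep contacting a few participants they might have dropped. The change cannot repair Day-28 losses that have already occurred; for those, the counts and reasons by arm that the SAP already asks for should be reported.
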